11.3 Efficacy Endpoints

The efficacy analysis will be conducted using the safety analysis set unless otherwise specified. The ORR/ DRR/ Disease control rate will be estimated with the associated exact 95% CI ([Clopper and Pearson, 1934](#)). Wilson's score method with continuity correction ([Newcombe, 1998](#)) will be used to calculate an approximation of the exact CI for between-group differences in binary rates. Kaplan-Meier (K-M) estimates of landmarks (e.g., 1-, 2-, and 3-year rates) and quartiles for DOR, time to treatment failure and OS will be provided ([Kaplan and Meier, 1958](#)) . Greenwood's formula ([Kalbfleisch and Prentice, 1980](#)) for standard error will be used to calculate CIs for landmark K-M rates. CIs for K-M quartiles will be estimated ([Brookmeyer and Crowley, 1982](#)). In addition, changes in tumor burden for responders will also be summarized.

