The main goals of the primary analysis are to evaluate the correlation between baseline intratumoral CD8+ cell density and ORR, DRR, DOR, and changes in tumor burden, in addition to the correlation between changes in **intratumoral** CD8+ cell density during treatment and ORR, DRR, DOR, and changes in tumor burden. The timing of the primary analysis will be when all subjects have had the opportunity to complete 12 months of treatment with talimogene laherparepvec.

An interim analysis to evaluate the study objectives will be conducted on approximately the first 50 subjects who received at least 1 dose of talimogene laherparepvec, with the biomarker recorded at baseline, and have had the opportunity to be in the study (treatment or follow-up) for 6 months.

The final analysis will occur **either 24 months after the last subject has been enrolled or** when the last subject discontinues the study treatment and has had the opportunity to complete the **safety follow-up, whichever is later.**

Descriptive statistics will be provided for demographic, safety, efficacy, and biomarkers as appropriate. In general, the safety analysis set will be used for all safety analyses. The safety analyses include incidence of treatment-emergent and treatment-related adverse events (all adverse events, \geq grade 3 adverse events, serious adverse events, fatal adverse events and adverse events defined as events of interest).

The efficacy analysis will be conducted using the safety analysis set as well, unless otherwise specified. The ORR will be estimated with the associated 95% CI. Descriptive statistics for DRR, time to treatment failure, changes in tumor burden, and OS will be provided. In addition, DOR and changes in tumor burden for responders will also be summarized.

The correlation between a baseline biomarker and response rate will be evaluated. The functional manner in which the response rate may vary with the biomarker is unknown; therefore multiple functional relationships may be examined. Pearson's correlation coefficient (r) will be estimated between the biomarker change and the maximum decrease in index lesions to evaluate the correlation between changes in a biomarker post-treatment and the effect of treatment on measurable lesions, in addition to correlating biomarker changes with objective response using logistic regression.

[figure not shown]
For further details on the statistical analysis, please refer to [Section 10](#).

Sponsor: Amgen Inc.

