1.2 Secondary

The secondary objectives are as follows:

- to explore the correlation between baseline intratumoral CD8+ cell density and durable response rate (DRR), duration of response (DOR), and changes in tumor burden
- to explore the correlation between changes in intratumoral CD8+ cell density during treatment and ORR, DRR, DOR, and changes in tumor burden
- to evaluate ORR, DOR, time to treatment failure (TTF), DRR, OS, and change in tumor burden during treatment
- to evaluate the safety and tolerability of talimogene laherparepvec

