10.4 Planned Methods of Analysis

Descriptive statistics will be provided for demographic, safety, efficacy, and biomarkers as appropriate. In general, the safety analysis set will be used for all safety analyses. The safety analyses include incidence of treatment-emergent and treatment related adverse events (all adverse events, \geq grade 3 adverse events, serious adverse events, fatal adverse events and adverse events defined as events of interest).

The efficacy analysis will be conducted using the safety analysis set as well unless otherwise specified. The ORR will be estimated with the associated 95% CI.

Descriptive statistics for DRR, time to treatment failure and OS will be provided. In addition, DOR and changes in tumor burden for responders will also be summarized.

The correlation between a baseline biomarker and response rate will be evaluated. The functional manner in which the response rate may vary with the biomarker is unknown; therefore multiple functional relationships may be examined. Pearson's correlation coefficient (r) will be estimated between the biomarker change and the maximum decrease in index lesions to evaluate the correlation between changes in a biomarker post-treatment and the effect of treatment on measurable lesions, in addition to correlating biomarker changes with objective response using logistic regression.

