All other lesions (or sites of disease), including any measurable lesions that were not chosen as index lesions will be identified as nonindex lesions. Nonindex lesions should be recorded and assessed qualitatively over the course of therapy.

Follow-up "Index Lesions":

At each subsequent tumor assessment, the SPD of the index lesions are added together to provide the total tumor burden.

Follow-up "Nonindex Lesions":

Nonindex disease measurements are not required and these lesions should be followed as "present," "absent," or in rare cases "unequivocal progression".

Response Criteria

Evaluation of Objective Response:

The subject response will be assessed based on the response of the index lesions and nonindex lesion, and presence or absence of new lesions. Confirmation of complete or partial response is not required. The overall response is derived from time point response assessments as described in [Table 5](#), [Table 6](#), and [Table 7](#).

Table 5. Definition of Index Lesion Tumor Response Including New Lesions

Complete Response (CR):	Complete disappearance of all index lesions, including any new tumors which might have appeared. Any residual cutaneous or subcutaneous index lesions must be documented by representative biopsy to not contain viable tumor.
Partial Response (PR):	Achieving a 50% or greater reduction in the SPD of the perpendicular diameters of all index lesions at the time of assessment as compared to the sum of the products of the perpendicular diameters of all index lesions at baseline. If any new lesions have appeared, the sum of products of the perpendicular diameters of new measurable lesions must have reduced by 50% or more from when first documented.

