4.1.2 Secondary Endpoints

- Correlation between a baseline immunoprofile (ie, intratumoral CD8+ cell density) and durable response rate (DRR), and duration of response (DOR), and changes in tumor burden
- Correlation between changes in an immunoprofile during treatment (in injected and uninjected lesions) and ORR, DRR, DOR, and changes in tumor burden
- Efficacy Endpoints: ORR, DOR, time to treatment failure (TTF), DRR, OS, and change in tumor burden during treatment
- Safety Endpoints: subject incidence of treatment-emergent and treatment-related adverse events (including all adverse events, grade ≥ 3 adverse events, serious adverse events, fatal adverse events, events of interest, adverse events requiring the discontinuation of study drug), clinically significant laboratory changes, and incidence of symptomatic herpetic lesions that are positive for talimogene laherparepvec

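### Change in tumor burden is an unrestricted secondary endpoint, but protocol 10.4 and SAP 11.3 name a summary of it only for responders, in conflict with the synopsis

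*SAP*

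**What the plan says.** The endpoint itself carries no restriction:

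- Protocol 1.2 gives the secondary objective "to evaluate ORR, DOR, time to treatment failure (TTF), DRR, OS, and change in tumor burden during treatment". SAP 4.1.2 lists "Efficacy Endpoints: ORR, DOR, time to treatment failure (TTF), DRR, OS, and change in tumor burden during treatment", as does protocol 10.1.1.2.
- The default population is all treated subjects. SAP 11.3: "The efficacy analysis will be conducted using the safety analysis set unless otherwise specified".

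The analysis text differs by place:

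- Protocol synopsis, Statistical Considerations: "Descriptive statistics for DRR, time to treatment failure, changes in tumor burden, and OS will be provided". The next sentence adds a summary in responders.
- Protocol 10.4: "Descriptive statistics for DRR, time to treatment failure and OS will be provided", followed by "In addition, DOR and changes in tumor burden for responders will also be summarized". This is the synopsis sentence without tumor burden; the responder sentence stays.
- Protocol 10.4.2 assigns Kaplan-Meier methods to OS, DOR and TTF, and confidence intervals to DRR and ORR. It gives no descriptive summary of tumor burden.
- SAP 11.3 gives a method for ORR, DRR, disease control rate, DOR, TTF and OS. For tumor burden it says "In addition, changes in tumor burden for responders will also be summarized".
- SAP section 12 lists two changes from the protocol, and this is not one of them. The Amendment 1 log records no edit to protocol 10.4 or to this synopsis sentence.

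**The concern.** Tumor burden is measured on the same quantity that defines response. Protocol Appendix D states "At each subsequent tumor assessment, the SPD of the index lesions are added together to provide the total tumor burden", and a partial response requires at least a 50% reduction in that index-lesion sum of products (SPD) from baseline. A summary confined to responders is therefore selected on the variable it reports. It says how far tumors shrank in subjects already known to have shrinking tumors. It does not say what happened to tumor burden during treatment, which is the objective.

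This matters here because protocol 3.1 expects some subjects to show transient growth or new tumors before benefit. A responder summary leaves out subjects who grow and never respond. It also leaves out subjects whose index lesions shrink by half but whose new measurable lesions do not, because Appendix D requires both for a partial response.

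**Working it through.** The documents give no figure for the tumor-burden summary, so there is none to reproduce. The 26.4% response rate used below also underlies the plan's 88% power for the one-sided Fisher test (50 versus 50, 13.2% versus 39.6%). Exact enumeration gives 0.884. That figure agrees with the plan and is not affected by this point.

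**Step 1: how many subjects the named summary covers.** Inputs are about 110 enrolled (protocol 3.3) and an assumed ORR of 26.4% (protocol 10.2), taking all enrolled subjects as treated.

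- Responders: 110 × 0.264 = 29.0
- Not covered: 110 − 29 = 81, or 73.6%

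**Step 2: what the response definition fixes.** Under Appendix D a partial response needs a fall in index SPD of at least 50%, and a complete response needs all index lesions to disappear. So at the response assessment each responder is at −50% or below. There are two exceptions. A complete response may rest on a residual lesion shown by biopsy to hold no viable tumor (Appendix D, Table 5), and a response may be assigned at surgery (protocol 6.5). The rule does not fix the depth beyond 50%, or the values before and after the response assessment.

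**Step 3: illustration of the gap between populations.** The documents give no distribution of tumor change, so this step is an assumption. Let the ratio of best on-treatment SPD to baseline SPD be lognormal, and treat any fall of at least 50% as a response (ignoring new lesions and the two exceptions). For log-scale standard deviation s, set the mean to μ = ln(0.5) − s·z, with z the normal quantile at 0.264, so that 26.4% of subjects respond. The all-subject median change is exp(μ) − 1. The responder median comes from simulation of the same model.

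| s | Median, all subjects | Median, responders |
|---|---|---|
| 0.4 | −36% | −59% |
| 0.7 | −22% | −64% |
| 1.0 | −6% | −69% |
| 1.5 | +29% | −76% |

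At s = 0.7, raising the true ORR from 10% to 50% moves the all-subject median from +23% to −50%, but the responder median only from −61% to −69%. The direction of this contrast follows from the selection in Step 2; its size depends on the assumed model.

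**The case against.** Four points on the other side carry weight.

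1. A reader might infer that the plan excludes non-responders outright. The text does not say so. The sentences in protocol 10.4 and SAP 11.3 are additive in form, and in the synopsis the same form follows an all-subject summary. In 10.4 and 11.3, however, no preceding sentence summarizes tumor burden, so the addition has nothing to add to. The conflict stands; a deliberate exclusion is not shown.

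2. General rules may reach the endpoint. SAP 11.1 prescribes the usual descriptive statistics for continuous variables on the safety set unless otherwise specified, and protocol 10.4 opens with a general promise of descriptive statistics for efficacy. Either may be meant to cover it. But the synopsis has the same general opening and still names tumor burden, and SAP 11.3 can be read as specifying otherwise. The text is at best ambiguous.

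3. Parts of SAP sections 6, 7, 11.1 and 11.4 are blacked out and 11.2 is not visible, so an all-subject summary elsewhere in the SAP cannot be excluded. The mismatch between the synopsis and protocol 10.4 involves no redaction, and the efficacy text of SAP 11.3 is readable.

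4. Tumor change in non-responders is not ignored altogether. Protocol 10.4 and 10.4.2 correlate biomarker change with maximum decrease in index lesions, without a responder restriction. That is a correlation in biomarker-evaluable subjects, assumed to number 55, and not a description of the endpoint.

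**Conclusion.** The point holds as a conflict in the plan: an unrestricted secondary endpoint, an all-subject summary in the synopsis, and readable analysis text in protocol 10.4 and SAP 11.3 that names a summary only for responders, with no declared change. Followed as written, it would describe the endpoint in about 29 of 110 subjects chosen on a fall of at least 50% in the same measure.

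A reader might go further and say that the reported change is fixed by selection. That is too strong. Selection sets the direction and a floor at the response assessment, while depth, earlier growth and later regrowth can still vary. A reader might also quote a particular gap between responders and all subjects. The documents give no distribution for non-responders, so the medians in the table are illustrative. Only the 29 of 110 and the 50% floor, with its biopsy and surgery exceptions, rest on the plan's own figures and definitions.

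The endpoint is descriptive and secondary, in a trial with no formal hypothesis testing. The primary endpoint and the sample size are unaffected. The correction is still worth making, because the summary as named cannot answer the stated objective.

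**What to change.** In protocol 10.4 and SAP 11.3, restore the synopsis wording, so that changes in tumor burden are summarized descriptively in all safety-analysis-set subjects with a post-baseline measurement. Report the number of treated subjects without one. Keep the responder summary and label it supplementary. A waterfall plot is optional. If the all-subject summary already stands in SAP text that cannot be read here, a cross-reference from 11.3 is enough.

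The cost is a change of wording in two places and one more table from data already collected. The tumor-burden figure will look less favorable than one based on responders alone.

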11.4 Correlation Between Clinical Response and Baseline/Change in Intratumoral CD8+ Cell Density

CCI [REDACTED]
[REDACTED]
[REDACTED]
[REDACTED]
[REDACTED]
[REDACTED]
[REDACTED]
[REDACTED].

CCI

11.4.3 Evaluation for Possible Confounding Effects

To investigate the possible confounding effects, multivariate models will also be built including CD8+ cell density subgroup and baseline covariates, such as disease stage, ECOG score, LDH elevation, and CD8+ cell density by covariate interaction terms in these models mentioned in [section 11.4.1](#).¹¹

© 2013 Pearson Education, Inc.

11.4.4 Exploratory Endpoints

Correlation between the changes in the population of tumor specific cytotoxic T-cells and immunoscores during treatment and clinical response will be assessed by the methods described in the supplementary SAP. **CCI**

11.5 Subject Accountability

The number of subjects enrolled will be tabulated by investigator sites. Subject disposition including screened, enrolled, treated and ended treatment, and completed safety follow-up visit will be summarized for all enrolled subjects.

11.6 Important Protocol Deviations

Important Protocol Deviation (IPD) categories are defined by the protocol team before the first subject's visit and updated during the IPD reviews throughout the protocol prior to database lock. These definitions of IPD categories, sub-category codes and descriptions will be used during the course of the protocol.

Eligibility deviations are defined in the protocol.

11.7 Analysis of Adverse Events

The Medical Dictionary for Regulatory Activities (MedDRA) version 16.1 or later will be used to code AEs to a system organ class (SOC) and a preferred term (PT) within the SOC. The CTCAE version 3.0 will be used to grade severity of AEs.

A table will be provided with a high-level summary of the subject incidence of any treatment-emergent adverse event and any treatment-emergent, treatment-related adverse event within the following categories: grade 3, grade 4, grades 3 or 4, fatal adverse events; serious; and leading to permanent discontinuation of protocol drug.

Additional subject incidence tables will be presented to describe the treatment-emergent and treatment-related adverse events (including all adverse events, grade ≥ 3 adverse events, serious adverse events, fatal adverse events, adverse events of interest, adverse events requiring permanent discontinuation of protocol drug, and local effects on the tumor[ie, pain, inflammation and ulceration]). Summaries of treatment-emergent and serious AEs occurring in at least 1% of the subjects by preferred term will be provided in descending order of frequency. The subject incidence summaries will be provided in 2 ways: within SOC subset by preferred term, and by decreasing order of preferred term frequency. In addition, adverse events and treatment-related adverse events will be tabulated by worst grade within SOC subset by preferred term.

Exposure-adjusted subject incidence and exposure-adjusted event rates may be estimated for specific AEs.

Listings will be provided for treatment-emergent and treatment-emergent, treatment-related adverse events (including all adverse events, serious adverse events, fatal adverse events, and adverse events requiring permanent discontinuation of protocol drug). In addition, screening SAEs prior to study Day 1 and all AEs > 30 days from last dose of study drug will be listed.

11.7.1 Adverse Events of Interest

Adverse events of interest are defined in a version-controlled Product Safety Analysis Plan (PSAP) for talimogene laherparepvec. The search terms of each event of interest (EOI) will be extracted based on the most recent version of the PSAP prior to the database snapshot for the primary analysis. Versions of the PSAP and MedDRA used for the EOI analysis will be documented in clinical study report(s). The subject incidence of treatment-emergent and treatment-emergent, treatment-related events of interest (including all events of interest, serious events of interest, non-serious events of interest) according to the EOI search strategy categories will be summarized.

Subject incidence of events of interest will also be summarized by EOI category and preferred term within EOI category. In addition, events of interest may be tabulated by worst grade within EOI category by preferred term. A table summarizing the incidence of all treatment-emergent adverse events of interest will also be provided by EOI category as a high level summary.

11.7.2 Detectable Talimogene Laherparepvec DNA per qPCR in Suspicious Lesions

The rate of detectable talimogene laherparepvec DNA per qPCR in suspicious lesions is defined as the number of cases of detectable talimogene laherparepvec DNA per qPCR from swabs collected from lesions that are suspected to be herpetic in origin divided by all swabs collected from these lesions. This rate will be calculated based on the Reactive Swab Analysis Set.

The subject incidence will be reported for positive qPCR for talimogene laherparepvec DNA detection in any swab of a lesion suspected to be herpetic in origin. The analysis will be based on the Reactive Swab Analysis Set. A detailed listing of qPCR results for subjects having a positive qPCR testing will be provided. In addition, a listing for all subjects in the Reactive Swab Analysis Set will be provided with reported treatment-emergent adverse events (including preferred term, verbatim term, start and end dates, duration, grade, seriousness, and relationship to IP), and qPCR result.

11.7.3 Reporting of Suspected or Known Unintended Exposure to Talimogene Laherparepvec and Herpetic Illness in Close Contacts and Healthcare Providers

Potential or known unintended exposure to talimogene laherparepvec, and any related suspected signs or symptoms in a subject's close physical contact, household member, caregiver, or healthcare provider will be reported. If consent of close contact or

healthcare provider is provided, the exposed individual may be asked to have a swab taken to evaluate for the presence of talimogene laherparepvec in suspicious lesions. The positive qPCR for talimogene laherparepvec DNA detection from suspicious lesions will be reported. These individual cases in secondary contacts will be reported with separate ID numbers to distinguish them from subjects' data. More details will be provided in a program-level SSAP for unintended exposure to talimogene laherparepvec.

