 - o previously known BRAF^{V600E/K} tumor status: BRAF^{V600E/K} tumor status result, obtained from a local laboratory prior to screening for this study will be acceptable and should be available within 28 days after enrollment
 - o previously unknown BRAF^{V600E/K} tumor status: Archived formalin-fixed paraffin-embedded tumor tissue (block or unstained tumor slide) from either the primary tumor or a metastatic lesion (as described above) will be analyzed at a local laboratory or submitted to the central laboratory within 28 days after enrollment for BRAF^{V600E/K} tumor status determination
- swabs of cold sores, vesicles, and other lesions suspected to be herpetic in origin (if any) for qPCR testing:
 - o subject should return to clinic within 3 days of the occurrence of a reportable lesion suspected to be herpetic in origin, such as cold sores or vesicles. The lesion should be evaluated by the investigator and swabbed if **herpetic** infection is suspected. A qPCR analysis will be performed on the swab sample to evaluate whether the talimogene laherparepvec DNA is detectable in the sample.
- blood sample for HSV serostatus (within 3 days prior to talimogene laherparepvec administration) at day 1 of week 1, week 6, and week 12.
- blood sample for biomarker analysis (within 3 days prior to talimogene laherparepvec administration) at day 1 of week 1, week 6, week 12 and week 24. Note: Lymphocyte subsets will be measured by flow cytometric determination **CCI**

- **all tumor biopsies in the study should be performed from easily accessible with or without ultrasound guidance cutaneous, subcutaneous or nodal lesions.** Tumor biopsy for biomarker analysis **should not be collected prior to the subject being enrolled. Tumor biopsy should be collected** (within 5 days prior to **first** talimogene laherparepvec administration) from one lesion at day 1 of week 1 and, if there are ≥ 2 lesions at baseline and one is left uninjected as described in [Section 6.2.1.1](#), from an uninjected lesion **within 7 days prior to talimogene laherparepvec injection** at day 1 of week 6. Also **within 7 days after documentation of disease progression (PDn or PDr) that resulted in treatment discontinuation**, from the **available and easily accessible for biopsy with or without ultrasound guidance cutaneous, subcutaneous or nodal** lesion responsible for **progression**

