10.1.1.2 Secondary Endpoints

- Correlation between baseline intratumoral CD8+ cell density and durable response rate (DRR), and duration of response (DOR), and changes in tumor burden
- Correlation between changes in intratumoral CD8+ cell density during treatment and ORR, DRR, DOR, and changes in tumor burden
- Efficacy Endpoints: ORR, DOR, time to treatment failure (TTF), DRR, OS, and change in tumor burden during treatment
- Safety Endpoints: subject incidence of treatment-emergent and treatment-related adverse events (including all adverse events, grade ≥ 3 adverse events, serious adverse events, fatal adverse events, events of interest, adverse events requiring the discontinuation of study drug), clinically significant laboratory changes, and incidence of symptomatic herpetic lesions that are positive for talimogene laherparepvec

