Deaths of all causes that occur any time during the study are defined as on-study deaths. This may include deaths that occur beyond the end of the treatment period. Note that this study has a long-term survival follow-up after the safety follow-up, deaths that occur after the study long-term survival follow-up will be reported in study, 20120139, which is the registry study for long-term follow up of clinical trial subjects who have completed talimogene laherparepvec treatment.

7. Analysis Subsets

Safety Analysis Set: The safety analysis set will include all subjects who have received at least 1 dose of talimogene laherparepvec. The efficacy analysis and safety analysis will be performed on the safety analysis set.

CCI

Reactive Swab Analysis Set

Subjects who are enrolled, receive at least one dose of talimogene laherparepvec, and have at least one swab sample collected from lesions that are suspected to be herpetic

in origin. This analysis set is used to examine the number of subjects with a lesion suspected to be herpetic, and detection of talimogene laherparepvec DNA by qPCR in lesions suspected to be herpetic in origin.

8. Covariates and Subgroups

The following covariates may be used to examine efficacy and safety in subgroups or in multivariate analyses:

- Region, if applicable (by countries)
- Age at baseline: < 50, ≥ 50; < 65, ≥ 65; < 75, ≥ 75 years
- Disease stage at baseline: IIIB and IIIC vs IVM1a vs IVM1b vs IVM1c
- Baseline LDH ≤ ULN vs > ULN
- Sex (Female vs Male)
- ECOG (0 vs 1)

9. Interim Analysis

No interim analysis is planned.

10. Data Screening and Acceptance

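### The planned subject incidence of virus-positive herpetic lesions is a proportion among swabbed subjects, not an incidence among treated subjects

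*SAP*

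**What the plan says.** Protocol 10.1.1.2 lists among the secondary safety endpoints the "incidence of symptomatic herpetic lesions that are positive for talimogene laherparepvec", and SAP 4.1.2 repeats it. The protocol's general rule for the analysis set is in 10.4: "In general, the safety analysis set will be used for all safety analyses". SAP 11.1 likewise makes the Safety Analysis Set (everyone with at least one dose) the default unless another set is specified.

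SAP 11.7.2 does specify another set, and it plans two summaries on it:

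- A per-swab rate: positive results "divided by all swabs collected from these lesions".
- A subject-level figure: "The subject incidence will be reported for positive qPCR for talimogene laherparepvec DNA detection in any swab of a lesion", where the lesion is one thought to be herpetic. The next sentence sets its basis: "The analysis will be based on the Reactive Swab Analysis Set".

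SAP section 7 defines that set as enrolled, treated subjects who "have at least one swab sample collected from lesions that are suspected to be herpetic" in origin. Swabbing is selective. Under Protocol 7.2.2 the subject returns to clinic with a reportable lesion; "The lesion should be evaluated by the investigator and swabbed if" herpetic infection is suspected.

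Protocol 10.4.3 says only that the qPCR swab results will be summarised descriptively.

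**The concern.** Incidence means the share of people at risk who have the event. Everyone who received the virus is at risk of a virus-positive lesion, including the subjects who never develop a suspicious one. Those subjects cannot enter the Reactive Swab Analysis Set, so they drop out of the denominator.

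The report would then show, under the same term used for the adverse event tables, a percentage with a different denominator. It could be read next to the other subject incidences in SAP 11.7, which default to the Safety Analysis Set, and it would not be comparable with them. It also carries no information on how often suspect lesions occur. What is at stake is the interpretation of one named secondary safety endpoint for a replicating virus.

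**Working it through.** The documents state no expected number of lesions, swabs or positives, so there is no planned figure to reproduce. The check is of the denominator, followed by an illustration.

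**Definitions.** Let N be the treated subjects (Safety Analysis Set), k those with at least one swabbed suspect lesion (Reactive Swab Analysis Set), and x those with any positive swab.

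- Planned figure (SAP 11.7.2 with section 7): x / k, the probability of being positive given that the subject was swabbed.
- Incidence among treated subjects: x / N = (k / N) × (x / k).
- Ratio of the two: (x / k) / (x / N) = N / k. It does not depend on x, and equals 1 only if every treated subject is swabbed.

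**Inputs.** N = 110, the approximate enrolment in SAP 3.2, assuming all enrolled subjects are dosed. The values of k (5 to 30) and x = 2 are assumptions. Intervals are exact (Clopper-Pearson) 95% CIs.

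| Swabbed, k (assumed) | Planned figure, 2/k | Incidence, 2/110 | Ratio, 110/k |
|---|---|---|---|
| 5 | 40.0% (5.3 to 85.3) | 1.8% (0.2 to 6.4) | 22 |
| 10 | 20.0% (2.5 to 55.6) | 1.8% (0.2 to 6.4) | 11 |
| 20 | 10.0% (1.2 to 31.7) | 1.8% (0.2 to 6.4) | 5.5 |
| 30 | 6.7% (0.8 to 22.1) | 1.8% (0.2 to 6.4) | 3.7 |

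Check of the identity at k = 10: 10/110 = 9.1% swabbed, times 2/10 = 20% positive among them, gives 1.8%.

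The planned figure is not just a rescaled incidence that a reader could correct by eye. Two positives among 10 swabbed and six among 30 swabbed both give 20%, yet the incidences are 2/110 = 1.8% and 6/110 = 5.5%.

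**Is the incidence planned elsewhere?** The adverse event tables in SAP 11.7 use the Safety Analysis Set by default, but they are built from coded terms. Protocol 7.2 says the qPCR results come from a central laboratory and are not entered on the eCRF. As described, those tables would count herpetic lesions reported as adverse events without separating the virus-positive ones. Parts of SAP section 7 are blacked out, but the set definition and the 11.7.2 text are readable.

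**The case against.** The strongest reply is that the SAP is entitled to do this. The protocol assigns the safety set only in general, SAP 11.1 allows exceptions, and 11.7.2 names its exception openly. The endpoint wording states no denominator, and 11.7.2 writes out a division only for the per-swab rate; for the subject-level figure the denominator is inferred from the named set. A proportion among swabbed subjects is a legitimate quantity. Nothing is lost either: SAP 11.7.2 requires a listing of positive subjects and another of everyone in the set, so dividing the positive count by the size of the safety set gives the incidence.

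Most of this stands, and it limits the harm. It does not remove the problem. Using the named set's size as denominator is the natural reading, and the result is then labelled as an incidence when it is not one. The figure the endpoint asks for is left for the reader to compute.

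Two stronger readings are tempting and are not supported:

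- A reader might infer that the subject-level figure is simply the swab positivity rate. It is not. The per-swab rate is a separate statistic in the same section, and the figure at issue counts each subject once.
- A reader might infer that the SAP will report a meaningless 100% of subjects with a suspect lesion. SAP section 7 plans a number of such subjects, not a percentage of the set, and a count is not made trivial by the restriction.

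**Conclusion.** As written, SAP 11.7.2 yields a subject-level positivity proportion among swabbed subjects and calls it a subject incidence. It does not deliver the incidence among treated subjects that the secondary safety endpoint calls for. The overstatement, if the figure is read as that incidence, is exactly the number treated divided by the number swabbed. This rests on the natural reading that the named set supplies the denominator.

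The factors of 22, 11, 5.5 and 3.7 rest on assumed swab counts and on all 110 subjects being dosed. They show how the ratio behaves; they are not a forecast, and the documents do not support citing any one of them as the size of the error.

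It would also go too far to treat this as a critical flaw. It concerns one descriptive secondary summary in a study without formal hypothesis testing, the numerator is correct, and the incidence can be recovered from planned listings. It should be fixed because the correction is simple and the endpoint is a named one.

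**What to change.** In SAP 11.7.2, report over the Safety Analysis Set the number and percentage of subjects with (a) any qPCR-positive swab and (b) any swabbed suspect lesion. Exact 95% CIs are optional, since SAP 11.7 plans none for other adverse event incidences.

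Add a note that suspect lesions that were not swabbed count as not positive, so (a) is a lower bound on the incidence of virus-positive lesions.

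Keep the Reactive Swab Analysis Set for the per-swab rate and for the subject-level positivity proportion, and label both as conditional on being swabbed.

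The cost is a few sentences in SAP 11.7.2 and added all-treated rows in one table. No new data or procedures are needed.
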